## ABBREVIATIONS

Term	Definition
ADR	Adverse drug reaction
BOR	Best overall response
CR	Complete response
DCR	Disease control rate
DOR	Duration of response
ECG	Electrocardiogram
ES	Evaluable analysis set
FAS	Full analysis set
IRC	Independent review committee
LE	Investigator evaluation
NE	Not evaluable
ORR	Objective response rate
OS	Overall survival
PD	Progressive disease
PD-L1	Programmed death ligand 1
PFS	Progression-free survival
PR	Partial response
PT	Preferred term
RECIST	Response evaluation criteria in solid tumors
SAS	Statistical analysis system
SD	Stable disease
SOC	System organ class
SS	Safety set
TEAE	Treatment-emergent adverse event
TTF	Time to treatment failure
TTP	Time to progression
TTR	Time to response

## 1. REVISION

This version is drafted based on the study protocol (version no.: 3.0, version date: 29 May, 2019).

Content	Before	After	Reason for Revision
Cover	1. The version number is 1.0 2. The version date is 31 Mar., 2020	1. The version number is 2.0 2. The version date is 10 Apr., 2021	Version upgrade
8. APPENDICES		Appendices 2-5 were revised	MedDRA has been upgraded to v24.0, based on which the preferred terms of adverse events in Appendices 2-5 were updated

## 2. INTRODUCTION

This statistical analysis plan is developed for a phase II study on the efficacy of PD-1 antibody SHR-1210 in combination with apatinib mesylate in patients with advanced hepatocellular carcinoma, which will provide specific statistical analysis and reporting methods or strategies. This statistical analysis plan is drafted based on the final version of the study protocol (version no.: 3.0, version date: 29 May, 2019).

The final draft of this plan will be completed before database locking and will be signed by various functional departments for confirmation.

This study will also explore the anti-HBV efficacy of the combination therapy as well as biomarkers for predicting response. Subjects who have abnormal HBV test results at baseline will undergo regular HBV titer and HBsAg tests during the study. Subjects who provide informed consent for biomarker sample collection will have their blood and tumor specimens collected at baseline and during the study, including possibly a baseline biopsy. Some results of the exploratory biomarker study will be reported separately and not included in this clinical study report. The results from the exploratory biomarker study may be combined and analyzed with biomarker data from other studies of the investigational drug to formulate a hypothesis which will be further validated in future studies.

## **2.2. Study Objectives**

### **2.2.1. Primary objectives**

- To evaluate the ORR of SHR-1210 in combination with apatinib mesylate in patients with advanced hepatocellular carcinoma.

### **2.2.2. Secondary objectives**

- To observe and evaluate the progression-free survival (PFS), duration of response (DOR), time to response (TTR), time to progression (TTP), disease control rate (DCR), overall survival (OS), as well as 6/9/12/15/18-month survival rates of SHR-1210 in combination with apatinib mesylate in patients with advanced hepatocellular carcinoma.
- To evaluate the safety of SHR-1210 in combination with apatinib mesylate in patients with advanced hepatocellular carcinoma.

### **2.2.3. Exploratory objectives**

- To explore the anti-HBV effect of SHR-1210 in combination with apatinib mesylate.
- To explore biomarkers for predicting response.

### **2.3. Sample Size**

This is a single-arm study with its primary efficacy endpoint being ORR. This study includes patients who have systemic first-line treatment failure and patients who have not received systemic first-line treatment. The sample sizes of patients in the two groups are respectively estimated based on the following assumptions.

#### **Patients with systemic first-line treatment failure**

Assuming that the standard treatment efficacy is no greater than 10%, that the efficacy of SHR-1210 in combination with apatinib mesylate is 25%, and that  $\alpha = 0.05$  (two-sided), 64 patients enrolled are able to achieve a power of at least 90%. If the dropout rate is 20%, 80 patients need to be enrolled.

In the late period of the trial, the number of patients who have systemic first-line treatment failure will be increased to 120 to observe the efficacy and safety of the investigational drug in more such patients.

#### **Patients who have not received systemic first-line treatment**

Assuming that the standard treatment efficacy is no greater than 15%, that the efficacy of SHR-1210 in combination with apatinib mesylate is 30%, and that  $\alpha = 0.05$  (two-sided), the enrollment of 56 patients can ensure that the half width of 95% confidence interval (CI) of overall ORR be no more than 12%.

### **3. STATISTICAL HYPOTHESIS AND DECISION RULE**

Statistical hypothesis for patients with systemic first-line treatment failure is as follows:

Null hypothesis:  $ORR = 10\%$

Alternative hypothesis:  $ORR \neq 10\%$

If the lower limit of 95% CI of ORR is greater than 10%, PD-1 antibody SHR-1210 in combination with apatinib can be considered effective in the treatment of advanced hepatocellular carcinoma with systemic first-line treatment failure.

The decision rule for patients who have not experienced systemic first-line treatment failure is as follows:

If the lower limit of 95% CI of ORR is greater than 15%, it suggests that PD-1 antibody SHR-1210 in combination with apatinib is effective in the treatment of advanced hepatocellular carcinoma without systemic first-line treatment failure.

## **4. STUDY ENDPOINTS**

### **4.1. Efficacy Endpoints**

Investigator evaluation is based on RECIST v1.1, and the independent review committee (IRC) is based on RECIST v1.1 and mRECIST to evaluate the following efficacy endpoints: ORR, DCR, TTR, TTP, DOR, and PFS; other efficacy endpoints include OS, 6/9/12/15/18-month survival rates, and TTF. In addition, new anti-cancer treatments mentioned in all efficacy endpoints do not include traditional Chinese medicine anti-cancer treatment with a duration of treatment of 14 days or less.

#### **4.1.1. Primary efficacy endpoints**

The primary efficacy endpoint in this study is objective response rate (ORR) assessed by IRC based on RECIST v1.1.

ORR: It refers to the proportion of all subjects whose best overall response (BOR) is assessed as complete response (CR) or partial response (PR) as per RECIST v1.1.

BOR refers to the best overall response assessed by IRC and recorded from the date of first administration to the date of first progression objectively recorded in accordance with RECIST v1.1 or to the date of initiation of new anti-cancer treatment (whichever occurs first). Subjects with first assessment as CR/PR should be reexamined 4 weeks later for confirmation. For subjects who have no recorded progression or initiation of new anti-cancer treatment, the BOR will be determined based on all efficacy assessment results.

#### **4.1.2. Secondary efficacy endpoints**

##### **4.1.2.1. Objective response rate (ORR)**

Secondary efficacy endpoints of ORR include the objective response rates assessed by the investigators based on RECIST v1.1 and by IRC based on mRECIST. Secondary efficacy endpoints of BOR include the best overall response assessed by the investigators based on RECIST v1.1 and by IRC based on mRECIST.

##### **4.1.2.2. Disease control rate (DCR)**

Disease control rate (DCR): It is defined as the proportion of all subjects receiving study treatment, whose BOR is assessed as CR, PR, and SD (SD occurs at least 6 weeks after first administration) by IRC or investigators as per RECIST v1.1 (or mRECIST).

#### **4.1.2.3. Time to response (TTR)**

Time to response (TTR): It is defined as the time from the date of first administration to the date of first recorded tumor response (assessed as per RECIST v1.1 or mRECIST) in subjects whose BOR is CR and PR.

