7. EVALUATIONS

7.1. Efficacy Evaluation

7.1.1. Efficacy indicators

The primary efficacy endpoint for this study is the objective response rate (ORR) as assessed by independent review committee (IRC) as per RECIST 1.1.

Objective response rate (ORR): The proportion of subjects with a best overall response (BOR) of complete response (CR) or partial response (PR) as per RECIST 1.1 criteria.

CR and PR must be verified at least 4 weeks \pm 7 days after their first presence.

Best overall response refers to the best response assessed by the IRC, or the best response from the date of first dose to the first documentation of progression as per RECIST 1.1 or to the start of a new anti-tumor treatment (whichever comes first).

For subjects without documented progression or new anti-tumor treatment, the best overall response will be determined on the basis of all efficacy assessments.

For subjects who continue SHR-1210 treatment beyond progression, the best overall response should be based on the efficacy assessment at the time of first documented progression as per RECIST 1.1.

Secondary efficacy endpoints include:

- Objective response rate as assessed by the investigator as per RECIST 1.1;
- Progression-free survival (PFS): The period of time from the date of first dose to the date of the first recorded tumor progression (according to RECIST v1.1 criteria, regardless of whether treatment is continued) or death of any cause (whichever comes first).

When determining PFS, clinical exacerbations without definite evidence of disease progression (as per RECIST 1.1) is not considered progression. For subjects who die without any prior reports of progression, the date of death is considered the date of progression. Subjects without disease progression or death will be censored on the date of their last evaluable tumor assessment. Subjects without tumor assessments during the study or death will be censored on their date of first dose. Subjects who discontinue the treatment for reasons other than disease progression (no subsequent tumor assessments) will be censored on the date of their last evaluable tumor assessment. Subjects without disease progression before starting a new anti-tumor therapy will be censored on the date of their last evaluable tumor assessment prior to the start of new anti-tumor therapy.

- Time to objective response (TTR) is defined as the period of time from the date of first dose to the first documented tumor response (as per RECIST 1.1).

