#### **4.1.2.5. Duration of response (DOR)**

Duration of response (DOR): It is defined as the time from the date of first recorded tumor response (RECIST v1.1 or mRECIST) to the date of first recorded tumor objective progression (RECIST v1.1 or mRECIST) or the date of death due to any cause, whichever occurs first, in subjects whose BOR is CR and PR.

Censoring rules:

- If there is no baseline tumor measurement or there is baseline tumor measurement with absence of post-baseline tumor evaluation, censoring will be based on the date of first administration.
- If the subject does not have PD or die prior to the termination of the study/cut-off date for analyses or dropout and is not using a new anti-cancer drug prior to PD or death, censoring will be based on the date of the last valid efficacy evaluation.
- If a new anti-cancer treatment has been initiated before PD or death, censoring will be based on the date of the last valid efficacy evaluation prior to the new anti-cancer treatment.
- For death or progression with the absence of two or more planned visits (two visits are planned to be conducted at 26 weeks after 12 cycles of first administration and at 18 weeks prior to 12 cycles), censoring will be based on the date of the last valid efficacy evaluation prior to death or progression.
- For death or PD with the absence of two planned visits after first administration, censoring will be based on the date of first administration.

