#### **5.4.2.5. Duration of response (DOR)**

See Section 4.1.2.5 for the definition of duration of response (DOR).

Secondary endpoint DOR is calculated in months by using the following formula: (DOR event date/censoring date - date of first response + 1) / 30.4375.

DOR is analyzed only in subjects who have the best overall response of tumor response after treatment. The ending date of response must be consistent with the date of PD of PFS or death.

Kaplan-Meier method is used to calculate the median DOR in each treated population.

Brookmeyer-Crowley method is used to estimate the two-sided 95% CI of median time, and the survival curve is drawn. The 6/9/12-month DOR rates are estimated by Kaplan-Meier method, and the corresponding 95% CIs are calculated using the log-log transformation according to normal distribution approximation with back transformation to CIs on the untransformed scale.

The response date is the date of the first observed response.

In addition, descriptive statistics such as the number of subjects, minimum, maximum, and quartile (Q1 and Q3) are used to summarize the DOR data. If the maximum values are the censoring data, they will be displayed in the form of "xx+". The number and percentage of subjects with DOR of at least 6/9/12 months are calculated. At the same time, the number and percentage of DOR events as well as the censoring number and percentage are calculated and classified according to the reason of censoring.

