### Appendix 1.2 Best Overall Response with CR and PR to be Confirmed

Overall Response at First Time Point	Overall Response at Subsequent Time Point	Best Overall Response
CR	CR	CR
CR	PR	SD, PD, or PR a
CR	SD	SD (provided minimum criteria for SD duration met, otherwise, PD)
CR	PD	SD (provided minimum criteria for SD duration met, otherwise, PD)
CR	NE	SD (provided minimum criteria for SD duration met, otherwise, NE)
PR	CR	PR
PR	PR	PR
PR	SD	SD
PR	PD	SD (provided minimum criteria for SD duration met, otherwise, PD)
PR	NE	SD (provided minimum criteria for SD duration met, otherwise, NE)
NE	NE	NE

Overall Response at First Time Point	Overall Response at Subsequent Time Point	Best Overall Response
CR = complete response, PR = partial response, SD = stable disease, PD = progressive disease, and NE = not evaluable.		
a : If a CR is truly met at first time point, then any disease seen at a subsequent time point, even disease meeting PR criteria relative to baseline, makes the disease PD at that point (since disease must have reappeared after CR). Best response would depend on whether minimum duration for SD is met. However, sometimes CR may be claimed but subsequent scans suggest small lesions were likely still present, so in fact the patient had PR, not CR at the first time point. Under these circumstances, the original CR should be changed to PR and the best response is PR.		

## Appendix 2

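### The SAP dates TTR and DOR from the first recorded response without requiring that it be the response later confirmed

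*SAP*

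**What the plan says.** **Who is analysed.** SAP 4.1.2.3 ends TTR at the "date of first recorded tumor response (assessed as per RECIST v1.1 or mRECIST) in subjects whose BOR is CR and PR". SAP 5.4.2.5 restricts DOR in the same way: "DOR is analyzed only in subjects who have the best overall response of tumor response after treatment".

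**What makes a BOR of CR or PR.** Confirmation is required. SAP 4.1.1 says "Subjects with first assessment as CR/PR should be reexamined 4 weeks later for confirmation", and protocol 7.1.1 says "CR and PR must be verified at least 4 weeks" (with a 7-day window) after they first appear. SAP Appendix 1.2, titled "Best Overall Response with CR and PR to be Confirmed", scores PR followed by SD as SD, and PR followed by PR as PR.

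**Which date is used.** For TTR, SAP 4.1.2.3 says: "It is defined as the time from the date of first administration to the date of first recorded tumor response". For DOR, SAP 4.1.2.5 says "It is defined as the time from the date of first recorded tumor response (RECIST v1.1 or mRECIST" and so on, ending at progression or death. SAP 5.4.2.5 adds: "The response date is the date of the first observed response". Protocol 7.1.1 likewise refers to the first documented response. None of these places ties the date to the response that was confirmed, and Appendix 1.2 has no dating rule for a subject who fails confirmation once and is confirmed later.

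**The concern.** Confirmation decides who enters the TTR and DOR analyses but not which date they use. The two can part in a subject whose first PR is not confirmed and who later has a PR that is. That subject is a confirmed responder through the later pair of scans, yet the literal wording dates the response from the earlier PR.

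For such a subject the literal date can only shorten TTR and lengthen DOR, so any effect favours the treatment. TTR and DOR are descriptive secondary endpoints of an uncontrolled trial, meant to characterise the responses counted in the ORR. Two programmers could both follow this SAP and derive different dates. The gap recurs in each version that SAP 4.1 calls for: investigator RECIST 1.1, IRC RECIST 1.1 and IRC mRECIST.

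**Working it through.** **1. Scan interval, checked against the plan's own figures.** Protocol 6.2 schedules imaging every 2 cycles (8 weeks) for 12 cycles, then every 3 cycles (12 weeks), with a window of 7 days either side. The SAP's two-missed-visit windows are 18 and 26 weeks.
- 2 × 8 + 2 × 1 = 18 weeks and 2 × 12 + 2 × 1 = 26 weeks, so both figures reproduce.
- Protocol 3.1 and SAP 2.1 instead give 2-week and 3-week intervals. These would yield 2 × 2 + 2 = 6 and 2 × 3 + 2 = 8 weeks. The 8- and 12-week intervals are used below.

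**2. Formulas (SAP 5.4.2.3 and 5.4.2.5).** TTR = (response date − first dose date + 1) / 30.4375. DOR = (event date − response date + 1) / 30.4375.

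**3. Early re-response: PR week 8, SD week 12, PR week 16, PR week 20.** BOR is PR through weeks 16 and 20.
- TTR, literal: (56 + 1) / 30.4375 = 1.87 months.
- TTR from the confirmed response: (112 + 1) / 30.4375 = 3.71 months.
- Shift: 56 / 30.4375 = 1.84 months, taken off TTR and added to DOR.
- With the 7-day windows: 42 / 30.4375 = 1.38 to 70 / 30.4375 = 2.30 months. At 12-week scans: 84 / 30.4375 = 2.76 months.

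**4. Later re-response: PR week 8, SD weeks 12 and 16, PR weeks 24 and 28, PD week 48.**

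| | Literal | From confirmed response |
|---|---|---|
| TTR | 57 / 30.4375 = 1.9 months | 169 / 30.4375 = 5.6 months |
| DOR | 281 / 30.4375 = 9.2 months | 169 / 30.4375 = 5.6 months |

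This subject crosses both the 6-month and the 9-month DOR counts that SAP 5.4.2.5 reports.

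**5. Effect on the group.** The share of responders with this pattern is not in the documents, so everything here rests on assumed inputs. Planned numbers give 0.25 × 120 + 0.30 × 56 = 46.8, about 47 responders.

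*Simple calculation.* It assumes an 8-week shift, first responses at weeks 8, 16 and 24 in 60%, 25% and 15%, and exponential DOR with a 9-month median.

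| Share affected | Mean TTR shorter by | Median DOR longer by | DOR ≥ 6 months higher by |
|---|---|---|---|
| 2% | 0.04 months | 0.04 months | 0.2 points |
| 5% | 0.09 months | 0.10 months | 0.5 points |
| 10% | 0.18 months | 0.19 months | 0.9 points |

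*Tumour-growth simulation.* It assumes log-size change with mean −0.20 and SD 0.35, slow regrowth, RECIST thresholds, and a confirmation scan 4 weeks after each new PR.
- With measurement error of 5%, 8% and 11%, the share affected is 7.4%, 10.5% and 8.8%. With 2–3% error it is 2–4%.
- Mean TTR, literal against confirmed, is 12.0 v 12.9, 12.5 v 13.7 and 12.6 v 13.6 weeks.
- The proportion with DOR of at least 26 weeks is 88.4 v 86.8%, 65.6 v 62.9% and 45.4 v 43.3%, so 1.6 to 2.7 points higher. 0.027 × 47 = 1.3, about one subject.
- Across the settings tried, median TTR stayed at 8 weeks. Median DOR was mostly unchanged and 4 weeks longer in two settings.

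The stable median TTR depends on clearly more than half of responders having their confirmed response start at the first scan. In the simple calculation, with 60% first recorded at week 8, it moved by 0.05, 0.15 and 0.39 months on average at 2%, 5% and 10% affected, because in some trials it jumped one scan interval.

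**The case against.** The strongest reply is that the SAP never says a failed response counts. Because the analysis is limited to confirmed responders, the first recorded response can fairly be read as the first scan of the qualifying response, as opposed to its confirmation scan. The wording also follows the RECIST excerpt in protocol Appendix 2, section 4.6.2, which starts response duration when the CR or PR criteria are first met. This stands to the extent that the defect is a missing qualifier. It does not remove the defect: the reference to the first observed response in SAP 5.4.2.5 makes the benign reading harder, and no text settles the PR, SD, PR, PR case.

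Three stronger readings are tempting, and the documents do not support them:
- *The plan has an express rule that unconfirmed responses count.* It has none, and a subject whose only response failed confirmation is in neither analysis.
- *SD time inside DOR is wrong in itself.* DOR ends only at progression or death, so SD scans after a confirmed response properly belong to it. Only the start date is at issue.
- *The efficacy conclusion is inflated.* ORR depends on BOR, not on the response date. PFS, OS and the decision rules in SAP 3 do not use that date either.

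It is also fair to say that the effect is small: a mean TTR change of up to about 1 week is similar to the 7-day imaging window.

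**Conclusion.** The point holds as a minor gap in the definition of two secondary endpoints. Taken literally, the response date for a subject confirmed only at a second attempt is a PR that the SAP's own table does not accept. For that subject TTR is too short, and DOR too long, by the gap between the two PRs: 1.84 months for re-response one 8-week scan later, or 112 / 30.4375 = 3.68 months for re-response at week 24.

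For the group, under assumed inputs, roughly 2–10% of responders are affected. Mean TTR is about 0.2–1 week shorter, and the proportion with DOR of at least 6 months is 0–3 points higher, about one subject. Median DOR is mostly unchanged. Median TTR is unchanged in the tumour-growth simulation, but could move by one scan interval if only slightly more than half of responders respond at the first scan. For every responder whose first response is confirmed, both readings give the same date.

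**What to change.** In SAP 4.1.2.3, 4.1.2.5 and 5.4.2.5, define the response date as that of *the first CR or PR that is subsequently confirmed (the earlier scan of the confirming pair)*. Apply it to investigator RECIST 1.1, IRC RECIST 1.1 and IRC mRECIST. A line under Appendix 1.2 for the PR, SD, PR, PR sequence would complete it.

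The cost is one phrase in three sections and the matching derivation. Protocol 11.3 allows the SAP to be revised and calls for a protocol change only where main or key factors such as the primary endpoint are involved. If the benign reading was intended, no result changes; otherwise TTR and DOR become slightly less favourable.

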#### **4.1.2.4. Time to progression (TTP)**

Time to progression (TTP): It is defined as the time from the date of first administration to the date of first occurrence of imaging PD (assessed by IRC or investigators as per RECIST v1.1 or mRECIST).

Censoring rules:

- If there is no baseline tumor measurement or there is baseline tumor measurement with absence of post-baseline tumor evaluation, censoring will be based on the date of first administration.
- If the subject does not have PD prior to the termination of the study/cut-off date for analyses or dropout and is not using a new anti-cancer drug prior to PD, censoring will be based on the date of the last valid efficacy evaluation.
- If a new anti-cancer treatment has been initiated before PD, censoring will be based on the date of the last valid efficacy evaluation prior to the new anti-cancer treatment.
- If death occurs before PD, censoring will be based on the date of the last valid efficacy evaluation prior to death.
- For PD after the absence of two or more planned visits (two visits are planned to be conducted at 26 weeks after 12 cycles of first administration and at 18 weeks prior to 12 cycles), censoring will be based on the date of the last valid efficacy evaluation prior to PD.
- For PD after the absence of two planned visits after first administration, censoring will be based on the date of first administration.

